10.5 Reporting Procedures: Prospective Arm

10.5.1 Adverse Events

Throughout the study, the investigator must record all grade 3 or higher events based on the “Division Of AIDS Table For Grading The Severity Of Adult And Pediatric Adverse Events” (Version 2.0, November 2014), not present at baseline, on the appropriate Adverse Event Form within 5 business days of identification of the event. If an event is present at baseline, is clearly documented, and does not change in severity throughout the study, it does not need to be captured on an Adverse Event Form. However, if the event resolves, or begins to resolve, and then worsens again to a grade 3 or higher, it must be captured on an Adverse Event Form.

Within 5 business days of recognition of an adverse event, the Study Coordinator or site investigator will:

- Complete an Adverse Event Form in the RedCap Database.
- Record information on the adverse event in the participant's medical chart.
- Provide follow-up information when it becomes available

10.5.2 Serious Adverse Events

Deaths and immediately life threatening SAEs must be reported in the Redcap Database within 1 business day after the site becomes aware of the event. All other SAEs must be reported within 3 business days of site awareness.

10.5.3 AE and SAE Recording/Documentation/Follow-up

Adverse events will be collected from the time treatment starts on Day 0 through the end of the study follow-up period. Serious Adverse Events will be collected during the treatment phase plus 30 days.

At each contact with the subject as outlined above, information regarding AEs will be elicited by appropriate questioning and examinations and will be immediately recorded on a source document. Source documents will include: progress notes, laboratory reports, consult notes, phone call summaries, survey tools and data collection tools. Source documents will be reviewed in a timely manner by the research team. The onset date, the end date, the severity of each reportable event, and the Investigator's judgment of the AEs relationship to SOF/LDV will also be recorded.

Adverse events will be followed at a minimum until resolution of the AE or a return to baseline laboratory value. SAEs that occur after the study follow-up period that are reported to and are assessed by the Investigator to be possibly, probably, or definitely related must be reported to the UCSF Project Manager and in the Redcap Database, as described above.

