Postmarketing cases of symptomatic bradycardia, including fatal cardiac arrest and cases requiring pacemaker intervention have been reported when amiodarone is coadministered with SOF/LDV FDC. Bradycardia has generally occurred within hours to days, but cases have been observed up to 2 weeks after initiating HCV treatment. Patients also taking beta blockers, or those with underlying cardiac comorbidities and/or advanced liver disease may be at increased risk for symptomatic bradycardia with coadministration of amiodarone. Bradycardia generally resolved after discontinuation of HCV treatment. The mechanism for this effect is unknown. Coadministration of amiodarone with SOF/LDV FDC is not recommended.

Rationale for the use of Interferon-free, all Oral Regimen

HIV-infected subjects seem to have lower responses to HCV treatment using interferon based regimens. Since HIV infection is by itself an immunoregulatory disease, it is believed that these subjects will have less optimal responses to immune based therapies. However, use of non-immune based directly acting antiviral therapies that do not rely on host immunity excessively, seem to work very well in HIV infected subjects. For example, HIV infected subjects respond to antiretroviral therapy regardless of baseline CD4 T cell counts. Hence, it is expected that HIV-infected subjects would have better rates of SVR when treated with non-immune based, directly acting agents for HCV. Second, we have previously demonstrated that HIV-infected subjects who control HIV replication by themselves without the aid of ART seem to have faster clearance than those subjects with similar CD4 T cell counts, but requiring ART to suppress HIV replication [28]. Third, we are using an extended treatment duration for these subjects (12 to 24 weeks). We believe this would allow us to maximize the rates of SVR for HIV infected pre and post liver transplant subjects in which relapse can be severe and associated with significant worsening of decompensation.[44]

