3.2 Prospective Arm

The cohort of pre-transplant patients with cirrhosis due to hepatitis C will be treated with SOF/LDV until LT or for a maximum of 24 weeks. Patients with and without HCC within Milan criteria are eligible. Another cohort of liver transplant recipients with recurrent HCV infection post liver transplant will also be treated with SOF/LDV for a period of 12 weeks (no cirrhosis) or 24 weeks (cirrhosis). Patients with fibrosing cholestatic hepatitis are eligible and will be treated for 12 weeks.

Starting with Day 0, all subjects will receive SOF/LDV for 12 or up to 24 weeks. The total amount of time required to complete all the study visits is approximately 56 - 68 weeks from the screening period through the end of the follow-up visits:

- Up to 8 weeks Screening period
- 12 or 24 week treatment period
- 12 and 24 week post-treatment follow-up visits (SVR12 and SVR24)
- 36 weeks post-treatment to assess late viral relapse

Subjects identified to have mutations leading to SOF or LDV resistance following sequencing and phenotypic analysis will be requested to return at 12-week intervals for up to 36 weeks to determine the time required for the resistant virus to return to background levels.

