7.9 Post treatment follow up visits

After discontinuation of the study drug, subjects will be followed at post-treatment Week 12 and 24. The visit windows are shown below

- Follow up visits (+/- 14 days)
- Post treatment optional liver biopsy -7 days / +30 days (but can be done outside this window at the investigator's or physician designee's discretion).

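### Prospective arm: section 10.5.3 stops SAE collection 30 days after treatment, leaving 138 to 222 days of follow-up with no SAE rule

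*Combined protocol and SAP*

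**What the plan says.** Section 10.5.3 contains three rules that do not fit together.

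- For adverse events: "Adverse events will be collected from the time treatment starts on Day 0 through the end of the study follow-up period".
- For serious adverse events, in the next sentence: "Serious Adverse Events will be collected during the treatment phase plus 30 days".
- For later events: "SAEs that occur after the study follow-up period that are reported to and are assessed by the Investigator" as at least possibly related must be reported to the project manager and entered in the database.

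The surrounding sections matter too. Section 10.1 makes any inpatient hospitalization arising from an adverse event an SAE, whatever its grade. Sections 10.2 and 10.5.1 require a record of events of grade 3 or higher throughout the study, and section 10.2 has the investigator judge every AE for seriousness. Section 10.5.2 sets reporting times of 1 business day for deaths and immediately life-threatening SAEs and 3 business days for other SAEs. Section 10.4 assesses causality only up to 30 days after the last dose.

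The end of follow-up is itself given in two ways. Section 3.2 lists "36 weeks post-treatment to assess late viral relapse". Section 7.9 says that "subjects will be followed at post-treatment Week 12 and 24", and the schedule in section 11.1 ends with a visit at 6 months or later.

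**The concern.** The more serious class of event has the shorter collection window. Read literally, a related SAE seven weeks after treatment falls under no SAE collection rule, while one that occurs after the participant has left follow-up must be reported. That ordering is unlikely to be intended.

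The period is not an idle one. Relapse is assessed after treatment ends, and section 1.1 says of these patients that "relapse can be severe and associated with significant worsening of decompensation". Both post-treatment visits in section 7.9 fall inside the gap. At stake are the completeness and consistency of late SAE counts. Sites could reasonably differ on whether a late admission is an SAE to be reported promptly, an AE to be entered within 5 business days, or only a note in the source record. With 10 to 20 prospective participants, a few events handled differently would change the safety summary.

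**Working it through.** **Length of follow-up.** The inputs are in section 3.2: "Up to 8 weeks Screening period", "12 or 24 week treatment period" and a last assessment 36 weeks after treatment. The stated total is 56 to 68 weeks.

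- With 36 weeks of follow-up: 8 + 12 + 36 = 56 and 8 + 24 + 36 = 68 weeks. This reproduces the stated range exactly.
- With 24 weeks of follow-up (section 7.9): 8 + 12 + 24 = 44 and 8 + 24 + 24 = 56 weeks. This does not.

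The stated total therefore rests on 36 weeks, but the visit list in section 7.9 stops at 24, so both are carried forward.

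**Length of the gap.** Gap = post-treatment follow-up in days − 30, with a month taken as 365.25/12 = 30.44 days.

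- 24 weeks: 168 − 30 = 138 days; 138/30.44 = 4.5 months; 138/168 = 82% of post-treatment follow-up.
- 36 weeks: 252 − 30 = 222 days; 222/30.44 = 7.3 months; 222/252 = 88% of post-treatment follow-up.

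The first post-treatment visit is due at week 12, day 84, or day 70 at the earliest with the 14-day window. That is 40 days or more after SAE collection stops.

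**What is still recorded inside the gap.** Setting the sections side by side:

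| Late event | Rule that applies | What is missing or unclear |
|---|---|---|
| New event of grade 3 or 4, or death (grade 5 in 10.3) | AE form within 5 business days (10.5.1); seriousness judged (10.2) | Whether the 1- and 3-business-day times (10.5.2) and daily committee notification of unexpected SAEs (16) apply |
| Hospital admission graded 1 or 2 | Serious by definition (10.1), but below the AE form threshold (10.2, 10.5.1) | No form required; source record only |
| Admission for a condition present at baseline, severity unchanged | Exempt from an AE form (10.5.1) | No form required; source record only |
| Related SAE after follow-up | Reportable (10.5.3) | Needs a causality judgement that 10.4 ends 30 days after the last dose |

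The first row shows that most late deaths and severe decompensations should reach the database. The second and third rows are where events can be lost. The third matters in this arm because pre-transplant participants enter with decompensated cirrhosis (section 5.2).

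**The case against.** The strongest reply is that late serious events are largely captured already. Sections 10.2, 10.3 and 10.5.1 bring in everything of grade 3 or higher through follow-up, with seriousness judged. Lower-grade events should still reach source documents, because section 10.5.3 has AEs elicited at each contact. Section 10.5.2 gives no end date, so its reporting times can be read as applying to late SAEs. Thirty days also matches the causality window in section 10.4 and the on-treatment definition in section 4.2.2, so it looks like a deliberate choice based on exposure.

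Much of this stands, and it rules out some stronger readings.

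- A reader might infer that SAEs go wholly uncollected for 82% to 88% of post-treatment follow-up. The documents do not support that. Those shares measure the time without an SAE rule, not the proportion of events lost.
- A reader might infer that the two arms become non-comparable on safety because survival in the retrospective arm has no 30-day cut. That does not follow. Prospective deaths are captured as grade 5 events through follow-up. Section 10.6 counts retrospective hospitalizations and anemia only while on DAA treatment. Sections 4.4 and 4.5 specify no between-arm safety comparison.
- A reader might infer that the main safety result is compromised. The primary safety endpoint in section 4.1.3, an AE that ends study drug for good, arises on treatment and is untouched.
- Section 1.1 says that relapse can worsen decompensation. It predicts no frequency.

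The reply does not remove the inconsistency. An exposure-based window explains the on-treatment analysis, but not why related SAEs become reportable again after follow-up. If that later sentence meant the 30-day window by its term for follow-up, it would use the term differently from the AE sentence in the same section. A source note is also not a database entry. That section 10.5.2 can be read either way is part of the problem.

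**Conclusion.** The point holds as a limited gap in the prospective arm and should be corrected. Section 10.5.3 leaves 138 days (24-week follow-up) to 222 days (36-week follow-up) with no SAE collection rule.

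The consequences are confined to three things: serious events below grade 3, admissions for baseline conditions of unchanged severity, and uncertain application of the expedited reporting times and daily notification. Section 10.4 also conflicts with the rule on related SAEs after follow-up.

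The size rests on two assumptions: that follow-up ends at one of the two nominal times, and that the 30 days run from the last dose. The documents give no basis for estimating how many events would be affected.

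**What to change.** 1. In section 10.5.3, collect SAEs from Day 0 through the end of study follow-up, and state that the section 10.5.2 reporting times apply throughout.
2. In section 10.4, extend the causality window to match, and allow a causality judgement for SAEs reported after follow-up, so that the last rule in section 10.5.3 can be applied. Changing section 10.5.3 alone would leave this conflict in place.
3. Keep last dose plus 30 days as the on-treatment analysis window in section 4.2.2, and tabulate SAEs after that date separately.
4. Reconcile section 3.2 with sections 7.9 and 11.1, so that the end of follow-up that closes the window is a single defined time.

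With steps 1 and 4 in place the gap is zero. The cost is a few sentences of amendment and a few more SAE forms in 10 to 20 participants, largely at post-treatment visits that are already planned.

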10.5.4 Adverse Events and Serious Adverse Events Exempt from Reporting

Elective hospitalizations or hospital admissions for the purpose of conduct of protocol mandated procedures are not to be reported as an SAE unless hospitalization is prolonged due to complications.

10.6 Reporting Procedures: Retrospective Arm

Adverse event and safety monitoring is not required for the retrospective arm since the retrospective arm only involves data collection and elastography for those who consent. Elastography is ultrasound based and is without adverse events. However, sites will be asked to record data on historical adverse events identified in the medical record for data analysis (hospitalizations during treatment with DAA therapy, anemia requiring transfusion or EPO during treatment with DAA therapy, and death) but the retrospective arm participants are exempt from ongoing safety monitoring.

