3.1 Retrospective Arm

Participating sites will collect clinical data on all of the HIV/HCV co-infected patients with decompensated liver disease (CPT >7 pre or post liver transplant) treated with sofosbuvir based DAA therapies since 1/2014 at their center. This will be done under IRB approved waiver of consent if possible so that all treated patients meeting the inclusion criteria can be included to avoid statistical bias. Data collected will mirror the data collected in the prospective arm. In addition, participants will be contacted to provide consent to return to the site for one visit for current liver staging to evaluate reversal of fibrosis (unless liver staging by Fibroscan or liver biopsy was done in the previous 12 months), and to be contacted in the future by the NIH Clinical Center for long term follow-up.

- Efficacy will be defined as HCV RNA undetectable \geq 12 weeks post end of sofosbuvir based DAA therapy.
- Safety and tolerability will be defined by
 - discontinuation rates
 - rates of hospitalization during DAA therapy
 - frequency of anemia requiring blood transfusion or EPO
 - survival.
- Reversal of decompensation: defined by CP score and MELD score at last follow-up (evaluated at time to event given the variability in length of follow-up post treatment)
- Reversal of fibrosis: defined by liver fibrosis by Fibroscan or biopsy at last follow-up (evaluated at time to event given the variability in length of follow-up post treatment)

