4.1.3 Safety Endpoints

The primary safety endpoint is any AE leading to permanent discontinuation of study drug(s).

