4.2.2 Safety Population

The primary analysis set for safety analyses will include subjects who received at least one dose of study drug.

On treatment data will be analyzed and defined as data collected from the first dose of study drug through the date of last dose of study drug plus 30 days.

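### Retrospective hospitalization and anemia are abstracted only during DAA therapy, 30 days short of the stated safety window, although the safety sample size of 50 needs both arms

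*Combined protocol and SAP*

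**What the plan says.** **Retrospective arm.** Section 3.1 lists four measures of safety and tolerability. One is "rates of hospitalization during DAA therapy". The others are discontinuation, anemia requiring transfusion or EPO, and survival, none with a stated window. Section 10.6 tells sites which historical events to record: "hospitalizations during treatment with DAA therapy, anemia requiring transfusion or EPO during treatment with DAA therapy, and death". That wording limits hospitalization and anemia to the treatment period and leaves death open-ended.

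**Safety analysis.** Section 4.2.2 defines one safety population and takes on-treatment data as "data collected from the first dose of study drug through the date of last dose of study drug plus 30 days".

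**Prospective arm.** Section 10.5.3 says "Serious Adverse Events will be collected during the treatment phase plus 30 days". Section 10.1 makes inpatient hospitalization an SAE criterion, so a prospective admission is captured through that tail. Other adverse events, recorded at grade 3 or higher, have a longer window: "Adverse events will be collected from the time treatment starts on Day 0 through the end of the study follow-up period".

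**Exemption.** Section 10.5.4, which falls under the prospective heading 10.5, says "Elective hospitalizations or hospital admissions for the purpose of conduct of protocol mandated procedures are not to be reported as an SAE", unless complications prolong the stay. Section 10.6 has no counterpart.

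**Sample size.** Section 4.1 calls 50 patients sufficient for the safety endpoints. Table 2 there gives a 92% chance of at least one event when the true probability is 5%. Section 3.0 expects 10 (up to 20) prospective and 40 or more retrospective patients.

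**The concern.** Table 2 treats the 50 patients as if each were watched for the same event over the same period. Under the collection rules they are not. A hospitalization two weeks after the last dose is recorded for a prospective patient and is not requested for a retrospective one, although 4.2.2 places it inside the on-treatment window. The protocol itself treats those 30 days as relevant to the drug, because causality in 10.4 is also assessed to 30 days after the last dose.

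The gap falls on the larger arm, and its direction is known: it lowers the observed event rate and so flatters safety.

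A second, smaller gap concerns which admissions count. Section 8.6 foresees transplant during a pre-transplant course, so the question will arise. The plan does not say how an elective admission is handled in the retrospective arm, or how a transplant admission is handled in either arm.

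**Working it through.** **1. Reproduce Table 2.** P(at least one event) = 1 - (1 - p)^50.

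| p | Table 2 | Recomputed |
|---|---|---|
| 0.01 | 39% | 39.5% |
| 0.05 | 92% | 92.3% |
| 0.10 | 99.5% | 99.5% |
| 0.15 | 99.97% | 99.97% |

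The table is correct for 50 patients observed over one common window.

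**2. Share of patients affected.** With 40 retrospective patients, 40/50 = 80% if 10 are enrolled prospectively and 40/60 = 67% if 20 are.

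**3. Share of the window not requested.** Let T be the treatment duration in days (84 or 168; full courses as in 6.3).

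- 12 weeks: 30/(84 + 30) = 30/114 = 26%
- 24 weeks: 30/(168 + 30) = 30/198 = 15%

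These are shares of observation time, not of events. Retrospective patients qualify with any treatment duration (5.1), and a shorter course makes the share larger.

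**4. Illustrative effect on a combined rate.** The documents give no event rates. Two assumptions are therefore needed: a constant hazard, and a risk p of 5% from first dose to last dose plus 30 days. The risk visible on therapy alone is p_on = 1 - (1 - p)^(T/(T + 30)).

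- 12 weeks: 1 - 0.95^(84/114) = 3.71%
- 24 weeks: 1 - 0.95^(168/198) = 4.26%

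With 40 retrospective and 10 prospective patients:

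- Combined rate, 12 weeks: (40 × 3.71% + 10 × 5%)/50 = 4.0%
- Combined rate, 24 weeks: (40 × 4.26% + 10 × 5%)/50 = 4.4%
- P(at least one), 12 weeks: 1 - (1 - 0.0371)^40 × 0.95^10 = 86.8%
- P(at least one), 24 weeks: 1 - (1 - 0.0426)^40 × 0.95^10 = 89.5%

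One common window would give 5% and 92.3%.

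**5. Range.** With 40 + 20 patients and p = 5%, the combined rate is 4.1% or 4.5%, and P(at least one) is 92.1% or 93.7%, against 95.4% with one window. For p from 5% to 30%, the relative reduction in the combined rate is:

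| Split | 12 weeks | 24 weeks |
|---|---|---|
| 40/10 | 18-21% | 10-12% |
| 40/20 | 15-17% | 9-10% |

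If the hazard falls after the last dose, the loss is smaller; if it rises, the loss is larger.

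**6. Exemption.** No arithmetic is possible, because the documents give no rate of elective or transplant admissions. Counting elective admissions in one arm only would push the retrospective hospitalization rate upward, opposite to the missing tail. The two effects cannot be netted.

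**The case against.** The strongest reply is that the arms were never meant to share these measures. Section 3.1 defines hospitalization and anemia rates for the retrospective arm only. Section 4.2.2 speaks of study drug, and section 8 describes the study agent for the prospective arm. On that reading the 30-day rule governs prospective data, and each arm follows its own definition. It is true that no section specifies a combined hospitalization or anemia rate; combining is inferred from the sample size. But 3.1 says retrospective data are to mirror prospective data, 4.2 uses a single safety population, and the safety justification in 4.1 depends on 50 patients, which neither arm is planned to supply alone.

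Several stronger readings are tempting and are not supported:

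- *All retrospective safety events stop at the last dose.* Death in 10.6 and survival in 3.1 have no end date, and 3.1 puts no window on anemia; only 10.6 does.
- *Transplant admissions are exempt prospectively but counted as drug toxicity retrospectively.* Section 10.5.4 does not name transplant, and it would cover one only if the admission were read as elective. Neither 3.1 nor 10.6 attributes retrospective events to the drug. This is an ambiguity in both arms, not a shown difference between them.
- *The primary safety endpoint is compromised.* Section 4.1.3 makes it an AE leading to permanent discontinuation, which the 30-day tail and the admission exemption hardly touch.

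**Conclusion.** The point holds for hospitalization and for anemia requiring transfusion or EPO. Followed as written, the plan does not request the last 30 days of its own safety window for roughly two thirds to four fifths of patients.

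The textual mismatch needs no assumption. The sizes do: full 12- or 24-week courses for the 26% and 15%; and a constant hazard, a 5% risk and a 40/10 split for the fall to about 4.0-4.4% and 87-90%. They illustrate a moderate understatement and are not estimates of what this cohort will show. They cover the window only, so for hospitalization the net bias is unknown until countable admissions are defined.

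This weakens the supporting safety description and the Table 2 claim for these events. It does not overturn the primary safety endpoint or the SVR12 analysis. It should be corrected before the retrospective data are analyzed, because definitions settled after the results are seen would carry less weight.

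**What to change.** - In 3.1 and 10.6, abstract hospitalization and anemia requiring transfusion or EPO from first dose to last dose plus 30 days.
- Write one definition of a countable admission for both arms, stating whether elective and transplant admissions count. This has to accompany the longer window: where treatment stops at transplant, as 8.6 describes, the stay after surgery falls in the added 30 days.
- Record the transplant date and the reason for discontinuation, so that transplant admissions and drug stops at transplant can be tabulated apart from AE-related ones. The retrospective schedule in 11.2 has no transplant entry.
- Report safety by arm, and combine arms only for identically defined events. Tie the Table 2 statement to those events.

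The cost is 30 more days of chart abstraction per retrospective patient and a few data fields. Section 6.3 already takes sites into the record at 3 months and at 6 or more months after treatment, so the added period lies within charts being opened anyway. The resulting rates may look slightly less favourable.
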